## 6. A Priori Statistical Methods

### 6.1. General Considerations

This Statistical Analysis Plan (SAP) describes analyses that will be utilized for the full clinical study report (CSR) for Study JAIM, at the time of JAIM primary outcome database lock. Analyses to be produced prior to the JAIM primary outcome database lock, for purposes of regulatory submissions, will be identified in the retained list of analyses. Additional safety analyses that integrate data from the originating studies will be specified in the integrated safety analysis plan (ISAP) for SLE. Any exploratory analyses will be described in a separate document. Statistical analysis of this study will be the responsibility of Eli Lilly and Company or its designee.

Not all displays described in this SAP will necessarily be included in the CSR. Not all displays will necessarily be created as a “static” display. Some may be incorporated into interactive display tools such as Spotfire instead of, or in addition to, a static display. Any display described in this SAP and not included in the CSR would be available upon request.

Throughout this document, references to analyses of corticosteroids refer to analyses of systemic corticosteroids, unless otherwise specified.

Statistical analyses of categorical safety and efficacy endpoints will be descriptive in nature.

Frequency counts and percentages by treatment arm (see [Table JAIM.6.1](#)) will be provided for the safety and efficacy endpoints. For non-model-based efficacy endpoints, 95% confidence intervals (CIs) for single proportions using the Wilson Score (Wilson, 1927; Newcombe, 1998) method will be utilized.

Unless otherwise stated, inferential statistical analyses (p-values and 95% CIs) which compare treatment groups will not be conducted.

For continuous efficacy and health outcomes endpoints the significance of within-treatment group changes from baseline will be evaluated by testing whether the treatment group least squares mean (LS mean) changes from baseline are different from zero; the 95% CI and the standard error for the LS mean change will also be displayed.

Change from baseline (defined in [Section 6.3](#)) will be calculated as the postbaseline (at that visit) value minus the baseline value. If all baseline values are missing for a particular variable, the change from baseline and percent change from baseline will not be calculated.

[Table JAIM.6.1](#) summarizes the treatment arms based on the treatment assigned in JAIM.

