Measure	Description	Variable	Derivation/Comment	Definition of Missing
	
labeled “best imaginable health state” and “worst imaginable health state.” This information can be used as a quantitative measure of health outcome.
 
The EQ 5D 5L health states, defined by the EQ 5D 5L descriptive system, may be converted into a single summary index by applying a formula that essentially attaches values (also called weights) to each of the levels in each dimension (Herdman et al. 2011; EuroQol Group 2015 [WWW]).
			
WPAI-Lupus	
The Work Productivity and Activity Impairment – Lupus (WPAI-Lupus) is a patient-reported instrument developed to measure the impact on work productivity and regular activities attributable to SLE. It contains 6 items that measure: 1) employment status, 2) hours missed from work due to the specific health problem, 3) hours missed from work for other reasons, 4) hours actually worked, 5) degree health affected productivity while working, and 6) degree health. Scores are calculated as impairment percentages (Reilly et al. 1993), with higher scores indicating greater productivity impairment.
	Employment Status	Yes/No	Missing if answer is missing
		Absenteeism Score (%)	$\frac{Q2}{(Q2 + Q4)} \times 100$	Missing if Q2 or Q4 are missing. Also missing if Employment Status is No.
		Presenteeism Score (%)	$\frac{Q5}{10} \times 100$	Missing if Q5 is missing. Also missing if Employment Status is No.
		Work productivity Loss Score (%)	$\left[ \frac{Q2}{Q2 + Q4} + \left( 1 - \frac{Q2}{Q2 + Q4} \right) \frac{Q5}{10} \right] \times 100$	Missing if Q2, Q4 or Q5 is missing. Also missing if Employment Status is No.
		Activity Impairment Score (%)	$\frac{Q6}{10} \times 100$	Missing if Q6 is missing. May still be present and nonmissing if patient is unemployed.

Abbreviations: BICLA = British Isles Lupus Assessment Group-based Composite Lupus Assessment; BILAG = British Isles Lupus Activity Group; CNS = Central Nervous System; FACIT = Functional Assessment of Chronic Illness Therapy; MCS= Mental Component Score; NRS = Numeric Rating Scale; PGA = Physician's Global Assessment; PCS= Physical Component Summary; SRI-4 = Systemic Lupus Erythematosus (SLE) Responder Index; SLEDAI-2K = Systemic Lupus Erythematosus Disease Activity Index 2000; SFI = SLEDAI Flare Index; SF-36 = Short Form 36; V = visit; VAS = Visual Analog Scale.

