CLASI Activity Score	The proportion of patients with $\geq 50\%$ reduction from baseline in total activity score	Descriptive analysis with observed and NRI	mITT – patients with CLASI total activity score $\geq 10$ at baseline	Week 156 visit
SFI	Annualized severe flare rate	Descriptive analysis with observed rate	mITT	Week 0 to Week 156 visit
	Annualized severe flare rate	Descriptive analysis with observed rate	mITT	Week 0 to Week 156 visit
	Annualized severe flare rate	Descriptive analysis with observed rate	mITT	Week 0 to Week 156 visit
SLICC/ACR Damage Index Score	Change from baseline in SLICC/ACR Damage Index	Descriptive analysis with observed and mLOCF	mITT	Week 156 visit
LLDAS	Proportion of patients who achieve a LLDAS	Descriptive analysis with observed and NRI	mITT, patients with SLEDAI score of $\geq 4$ at baseline	Week 156 visit
Corticosteroid Sparing	Change from baseline in prednisone dose	MMRM	mITT	Week 156 visit
Worst Pain NRS	Change from baseline in Worst Pain NRS	MMRM	mITT	Week 156 visit
FACIT-Fatigue	Change from baseline in FACIT-Fatigue total score	MMRM	mITT	Week 156 visit
Worst Fatigue NRS	Change from baseline in Worst Fatigue NRS	MMRM	mITT	Week 156 visit
Worst Joint Pain	Change from baseline in Worst Joint Pain NRS	MMRM	mITT	Week 156 visit
Patient Global Impression of Severity	Change from baseline in Patient Global Impression of Severity	MMRM	mITT	Week 156 visit
SF-36 V2 acute	Change from baseline in mental component score (MCS)	MMRM	mITT	Week 156 visit
	Change from baseline in physical component score (PCS)	MMRM	mITT	Week 156 visit
	Change from baseline in domain scores SF-36 health survey version 2 acute	MMRM	mITT	Week 156 visit
EQ-5D-5L	Change from baseline in EQ-5D-5L US/UK population-based index scores and VAS.	MMRM	mITT	Week 156 visit
	Proportion of patients with no problem in each EQ-5D-5L item score	Descriptive analysis with observed and NRI	mITT	Week 156 visit

Measure	Variable	Analysis Method	Population	Key Time Point(s) a
WPAI-Lupus	Change from baseline in WPAI-Lupus	MMRM	For absenteeism score, presenteeism score, and work productivity loss score, population is a subset of mITT that includes patients who had an employment status of Yes at baseline. For activity impairment score, use mITT population	Week 156 visit

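### The WPAI-Lupus missing-data rule can discard a work productivity loss score that the SAP's own formula fixes at 100%, for employed patients who worked no hours and left Q5 blank

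*SAP*

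**What the plan says.** SAP Table JAIM.6.3 numbers the WPAI-Lupus items. Q2 is hours missed because of the health problem. The next two that matter are "4) hours actually worked, 5) degree health affected productivity while working". Writing A = Q2/(Q2 + Q4), the table defines absenteeism as A × 100 and work productivity loss as [A + (1 − A) × Q5/10] × 100.

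The missing-data rules differ between the two rows:
- Absenteeism: "Missing if Q2 or Q4 are missing. Also missing if Employment Status is No".
- Work productivity loss: "Missing if Q2, Q4 or Q5 is missing. Also missing if Employment Status is No".

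Neither rule makes an exception for zero hours worked.

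In Table JAIM.6.4 the variable is "Change from baseline in WPAI-Lupus", analysed by MMRM. The three work-related scores use the part of the mITT population that "includes patients who had an employment status of Yes at baseline". SAP Section 6.4.2.3 assumes data are missing at random. SAP Section 6.1 adds that "If all baseline values are missing for a particular variable, the change from baseline and percent change from baseline will not be calculated", and Section 6.3 takes the efficacy baseline as the last nonmissing pre-treatment measurement. Appendix 2 also lists the score among the baseline summaries. The protocol (Table JAIM.2) makes WPAI-Lupus a secondary endpoint.

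**The concern.** Q5 asks about productivity during hours worked, so a patient who worked no hours has nothing to rate and may leave it blank. The table would then record that all work was missed yet treat overall work loss as unknown, although the formula already determines it.

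The value lost is the top of the scale. A blank that arises because no hours were worked depends on the score itself. The MMRM in SAP Section 6.4 conditions on the baseline value, the stratification factors and the patient's other visits of the same score. It does not use the absenteeism result that would reveal the missing value, so it predicts these records as if they came from patients who had worked. At stake are the visit means, the baseline summary, and the within-arm LS mean changes with their confidence intervals and p-values.

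**Working it through.** The documents state no WPAI mean, sample size or missing rate, so there is no planned figure to reproduce. The check has three parts.

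**1. The formula at zero hours worked.** With Q2 > 0 and Q4 = 0, A = Q2/(Q2 + 0) = 1. The score is [1 + 0 × Q5/10] × 100 = 100. Evaluating Q2 = 8, 20, 40 against Q5 = 0, 5, 10 gives 100.0 in all nine cases. Q5 does matter once any hours are worked: with Q2 = 35 and Q4 = 5, A = 0.875 and the score runs from 87.5 (Q5 = 0) to 100.0 (Q5 = 10). So the missing rule is reasonable in general and wrong only at Q4 = 0 with Q2 > 0. At Q2 = Q4 = 0 the formula is 0/0, which the table does not address.

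**2. Effect on a visit mean.** Let f be the share of employed patients with Q2 > 0, Q4 = 0 and Q5 blank, and m the mean score of the others. Neither is in the documents. The full mean is (1 − f)m + 100f and the rule reports m, so the understatement is f × (100 − m).
- f = 1%, m = 30: 0.01 × 70 = 0.7 points.
- f = 5%, m = 30: 0.05 × 70 = 3.5 points.
- Wider assumptions: f = 1%, m = 50 gives 0.01 × 50 = 0.5; f = 10%, m = 20 gives 0.10 × 80 = 8.0.

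**3. Effect on mean change from baseline.** Use subscript 0 for baseline and 1 for post-baseline. Take losses at the two times as independent, with no earlier baseline value to fall back on. The observed change is m1 − m0. Its bias (observed minus full-data) is f0(100 − m0) − f1(100 − m1). With assumed m0 = 45 and m1 = 35 the rule always reports −10.0:

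| f0 | f1 | Full-data change | Bias |
|---|---|---|---|
| 5% | 5% | −9.5 | 2.75 − 3.25 = −0.5 |
| 8% | 2% | −13.1 | 4.40 − 1.30 = +3.1 |
| 2% | 5% | −7.85 | 1.10 − 3.25 = −2.15 |

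With m0 = 35 and m1 = 30 the values tried ran from −3.5 (f0 = 0, f1 = 5%: 0 − 0.05 × 70) to +3.8 (f0 = 8%, f1 = 2%: 5.2 − 1.4). A negative bias overstates improvement; a positive one understates it.

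A simulation with correlated baseline and post-baseline scores (400,000 patients, simple mean change rather than an MMRM fit) showed the same pattern. True versus observed change was −8.71 versus −9.51 with about 8% at 100 at both times. It was −10.90 versus −8.36 with 8.1% at baseline and 2.2% afterwards, and −7.18 versus −10.70 with 2.3% and 8.2%.

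**The case against.** The strongest objection is that the premise is not documented. The protocol (Section 9.1.1.11.7) and SAP say the questionnaire is completed on a tablet but do not say whether Q5 is skipped at Q4 = 0 or whether the device forces an answer. If Q5 is always answered, the formula returns 100 and nobody is lost. This stands, and it makes the point conditional.

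Several stronger readings are tempting, and the documents do not support them:
- *The planned result is biased in a known direction.* Only the visit mean has a fixed direction. The endpoint is change from baseline, and part 3 shows either sign.
- *The most impaired patients leave the analysis at baseline.* Because baseline is the last nonmissing value, a lost score may be replaced by an earlier one. The patient leaves only if none exists. The documents do not show how often WPAI was collected in the originating studies.
- *The rule removes only the worst scores.* It also voids records with Q5 blank and Q4 > 0, or with Q2 or Q4 blank. It keeps some scores of 100, such as Q5 = 10 with Q4 > 0.
- *The table contradicts itself.* Requiring every item in a formula is an ordinary complete-item rule, and absenteeism does not use Q5. The result is an avoidable mismatch in one corner case, and the lost week still appears in the absenteeism results.

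None of this defends the rule at Q4 = 0. The SAP already makes the matching exception elsewhere: in the same table, a missing visit domain does not void the no-BILAG-worsening result when that domain was A at baseline, since it could not count as worsening.

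**Conclusion.** The point holds in conditional form. It is certain, from the SAP's own formula, that the score is 100% when Q2 > 0 and Q4 = 0, and that the stated rule discards it when Q5 is blank. Whether such blanks occur is an inference from the item wording. If they do, visit means, including the baseline summary, are understated. Change from baseline is biased in a direction that depends on whether the losses fall mainly before or after baseline. Missing at random does not cure either effect.

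The 0.7 to 3.5 points for a visit mean rest entirely on the assumed 1% to 5% affected and the assumed mean of 30%. They also count every affected patient as having a blank Q5. Impact is low: one of four WPAI scores, a secondary outcome in a study whose primary objective is safety, restricted to patients employed at baseline, with no between-arm testing planned.

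**What to change.** Replace the missing-data entry for the work productivity loss score in SAP Table JAIM.6.3 with a rule to this effect:

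- If Q2 > 0 and Q4 = 0, the score is 100%, whether or not Q5 was answered.
- In every other case the score is missing when any of Q2, Q4 or Q5 is blank, or when Q2 + Q4 = 0.
- The score remains missing when employment status is No.

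Leave the presenteeism rule as it is. Absenteeism has the same undefined 0/0 case and can take the same clause. Report by visit and arm how many records the first line affects, so a reader can see whether it mattered.

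The cost is one line of derivation and one count, with no new data. If Q5 is always answered, the scores do not change. The scoring source that the SAP cites was not available for this review and should be checked for consistency before the rule is adopted.

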**Table JAIM.6.4. Description of Efficacy/Health Outcomes Analyses**

Measure	Variable	Analysis Method	Population	Key Time Point(s) a
SRI-4	Proportion of patients achieving SRI-4 response	Descriptive analysis with observed and NRI	mITT, patients with SLEDAI-2K score of $\geq 4$ at baseline	Week 156 visit
SRI-x (where x is 5, 6, 7, 8)	Proportion of patients achieving SRI-x response	Descriptive analysis with observed and NRI	mITT, patients with SLEDAI-2K score of $\geq x$ at baseline	Week 156 visit
SLEDAI-2K	Change from baseline in mean total SLEDAI-2K through Week 156	MMRM	mITT	Week 156 visit
	Proportion of patients achieving reduction of $\geq 4$ points from baseline	Descriptive analysis with observed and NRI	mITT, patients with SLEDAI-2K score $\geq 4$ at baseline	Week 156 visit
	Proportion of patients with improvement in each SLEDAI-2K individual organ systems vs baseline	Descriptive analysis with observed and NRI	mITT, patients with SLEDAI-2K score $> 0$ within the organ domain at baseline	Week 156 visit
	Proportion of patients with worsening in each SLEDAI-2K individual organ system vs baseline	Descriptive analysis with observed and NRI	mITT, patients with at least 1 SLEDAI-2K item = 0 in the organ domain at baseline	Week 156 visit
BILAG	Proportion of patients with no new BILAG A and no more than 1 new BILAG B disease activity score (compared with baseline)	Descriptive analysis with observed and NRI	mITT	Week 156 visit
	Proportion of patients with improvement in each BILAG individual organ system vs baseline	Descriptive analysis with observed and NRI	mITT, patients with BILAG A or B in the organ domain at baseline	Week 156 visit
	Proportion of patients with worsening in each BILAG individual organ system vs baseline	Descriptive analysis with observed and NRI	mITT, patients without BILAG A in the organ domain at baseline	Week 156 visit
PGA	Proportion of patients with no worsening in PGA (compared with baseline)	Descriptive analysis with observed and NRI	mITT	Week 156 visit
	Change from baseline in PGA score over time through Week 156	MMRM	mITT	Week 156 visit
BICLA	Proportion of patients achieving BICLA response	Descriptive analysis with observed and NRI	mITT	Week 156 visit
28 Tender/Swollen Joint Count	Change from baseline in tender joint count	MMRM	mITT	Week 156 visit
	Change from baseline in swollen joint count	MMRM	mITT	Week 156 visit

Measure	Variable	Analysis Method	Population	Key Time Point(s) a
CLASI Activity Score	The proportion of patients with $\geq 50\%$ reduction from baseline in total activity score	Descriptive analysis with observed and NRI	mITT – patients with CLASI total activity score $\geq 10$ at baseline	Week 156 visit
SFI	Annualized severe flare rate	Descriptive analysis with observed rate	mITT	Week 0 to Week 156 visit
	Annualized severe flare rate	Descriptive analysis with observed rate	mITT	Week 0 to Week 156 visit
	Annualized severe flare rate	Descriptive analysis with observed rate	mITT	Week 0 to Week 156 visit
SLICC/ACR Damage Index Score	Change from baseline in SLICC/ACR Damage Index	Descriptive analysis with observed and mLOCF	mITT	Week 156 visit
LLDAS	Proportion of patients who achieve a LLDAS	Descriptive analysis with observed and NRI	mITT, patients with SLEDAI score of $\geq 4$ at baseline	Week 156 visit
Corticosteroid Sparing	Change from baseline in prednisone dose	MMRM	mITT	Week 156 visit
Worst Pain NRS	Change from baseline in Worst Pain NRS	MMRM	mITT	Week 156 visit
FACIT-Fatigue	Change from baseline in FACIT-Fatigue total score	MMRM	mITT	Week 156 visit
Worst Fatigue NRS	Change from baseline in Worst Fatigue NRS	MMRM	mITT	Week 156 visit
Worst Joint Pain	Change from baseline in Worst Joint Pain NRS	MMRM	mITT	Week 156 visit
Patient Global Impression of Severity	Change from baseline in Patient Global Impression of Severity	MMRM	mITT	Week 156 visit
SF-36 V2 acute	Change from baseline in mental component score (MCS)	MMRM	mITT	Week 156 visit
	Change from baseline in physical component score (PCS)	MMRM	mITT	Week 156 visit
	Change from baseline in domain scores SF-36 health survey version 2 acute	MMRM	mITT	Week 156 visit
EQ-5D-5L	Change from baseline in EQ-5D-5L US/UK population-based index scores and VAS.	MMRM	mITT	Week 156 visit
	Proportion of patients with no problem in each EQ-5D-5L item score	Descriptive analysis with observed and NRI	mITT	Week 156 visit

Measure	Variable	Analysis Method	Population	Key Time Point(s) a
WPAI-Lupus	Change from baseline in WPAI-Lupus	MMRM	For absenteeism score, presenteeism score, and work productivity loss score, population is a subset of mITT that includes patients who had an employment status of Yes at baseline. For activity impairment score, use mITT population	Week 156 visit

Abbreviations: BICLA = British Isles Lupus Assessment Group-based Composite Lupus Assessment; BILAG = British Isles Lupus Activity Group; CNS = Central Nervous System; EQ-5D-5L = European Quality of Life5 Dimensions–5 Level; FACIT = Functional Assessment of Chronic Illness Therapy; mLOCF = modified last observation carried forward; mITT = modified intent-to-treat; MMRM = mixed model for repeated measures; NRI = non-responder imputation; NRS = Numeric Rating Scale; PCS = Physical Component Summary; SRI-4 = Systemic Lupus Erythematosus (SLE) Responder Index; SLEDAI-2K = Systemic Lupus Erythematosus Disease Activity Index 2000; SF-36 = Short Form 36; WPAI-Lupus = Work Productivity and Activity Impairment Questionnaire: Lupus V2.0.

a Assessments collected at multiple visits will be analyzed at each visit, in addition to the key time point listed below.

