## 6.4. Analysis Methods

Continuous efficacy and health outcome variables, except for Systemic Lupus International Collaborating Clinics (SLICC)/American College of Rheumatology (ACR) Damage Index will use a restricted maximum likelihood-based mixed model for repeated measures (MMRM) analysis. The response variable will be change from baseline across postbaseline visits. The model will include the following explanatory variables as fixed factors: treatment, baseline disease activity (total SLEDAI-2K  $<10$ ;  $\geq 10$ ), baseline corticosteroid dose ( $<10$  mg/day;  $\geq 10$  mg/day prednisone or equivalent), region (North America, Central/South America/Mexico, Europe, Asia and Rest of World), visit (as categorical variable), baseline value, treatment-by-visit interaction, and baseline value-by-visit interaction. Within-patient variance-covariance errors will be modeled using an unstructured covariance matrix. If this analysis fails to converge, the following structures will be tested in this pre-specified order: 1) heterogeneous Toeplitz (TOEPH), 2) heterogeneous autoregressive (ARH[1]), 3) heterogeneous compound symmetry (CSH), and 4) autoregressive (AR[1]). The Kenward-Roger method will be used to estimate the degrees of freedom. For each treatment group the least squares mean (LS mean), standard error, within-treatment p-value, and 95% CIs will be reported.

Systemic Lupus International Collaborating Clinics (SLICC)/ACR Damage Index change from baseline will be summarized with observed and modified last observation carried forward (mLOCF).

The binary efficacy measures will be summarized with observed case and non-responder imputation (NRI).

For both efficacy and safety evaluations, if study drug is temporarily interrupted (suspended) during a treatment period, the measurements taken during the temporary interruption will be included in the analysis.

Both observed and imputed analyses will be performed for efficacy and health outcomes measures.

All analyses will include the treatment arms given in [Table JAIM.6.1](#).

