#### **6.4.2.2. Non-responder Imputation (NRI)**

The NRI method may be used when the estimand of interest uses the composite strategy (EMA 2020) for handling intercurrent events. In this strategy, patients with any intercurrent event that leads to the permanent discontinuation of assigned study treatment or to prohibited medication use are defined to have failed treatment for that particular visit interval but not for the subsequent visit intervals (as defined in Section 6.4.2). Therefore, using a composite estimand approach, no data would be missing and the function of the NRI is to estimate the estimand.

All patients who discontinue the study or permanently discontinue study treatment at any time for any reason or patients who have a prohibited medication in a particular visit interval will be defined as non-responders for that visit interval and excluded from the subsequent visit intervals. Enrolled patients without at least one postbaseline observation will be defined as non-responders for the first visit interval (Visit 6) and excluded from evaluation in subsequent visit intervals.

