## **6.11. Efficacy Analyses**

### **6.11.1. General Considerations**

[Table JAIM.6.3](#) includes the description, derivation and definition of missingness of the efficacy and health outcomes measures and endpoints. [Table JAIM.6.4](#) includes the description of the

analysis method, population and primary time point(s) of analysis for efficacy and health outcomes measures. Assessments collected at multiple visits will be analyzed at each visit, in addition to the primary time point. Details of each analysis will follow the general principles described under Analysis Methods in Section [6.4](#).

Table JAIM.6.3. Description and Derivation of Efficacy/Health Outcomes Measures and Endpoints

Measure	Description	Variable	Derivation/Comment	Definition of Missing
SRI-4	SRI-4 is a composite index to measure overall improvement in disease activity (SLEDAI-2K) while ensuring there is no worsening in other organ systems (BILAG and PGA)	SLE Responder Index 4	A decrease in SLEDAI-2K $\geq 4$ (from baseline), and No new BILAG A and no more than 1 new BILAB B organ domain (both compared with baseline), and No worsening in PGA (defined as an increase of 0.3 points [10 mm] from baseline).	Missing, if any component (SLEDAI, BILAG, or PGA) remains missing after each instrument-level imputation rule is applied
SLEDAI-2K	The SLEDAI-2K is a global disease activity instrument that focuses on high-impact disease manifestations across 9 organ domains: constitutional, mucocutaneous, musculoskeletal, vascular, cardiorespiratory, central nervous system, immunologic, renal, and hematologic.	SLEDAI-2K Total Score	Calculated by summing the weighted organ manifestations. For the Renal domain, when the urinary casts, hematuria, and pyuria items are “not done” or “not accessed”, they will be coded as “not present”.	If any item scores or all items are missing (not done or not assessed), but the visit occurred, data for that item can be carried forward if obtained within the previous 36 days of visit.
		Individual Organ Domain Improvement defined by SLEDAI-2K	Among patients with SLEDAI-2K score $>0$ within the organ domain at baseline and able to decrease SLEDAI-2K (from baseline) within each organ domain score, separately.	Missing if any SLEDAI-2K item for that organ domain remains missing after instrument-level imputation rules are applied.

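### Does the SAP leave open whether a non-responder counts as worsened in the two organ-worsening rows of Table JAIM.6.4?

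*SAP*

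**What the plan says.** SAP Section 6.4 applies observed-case and NRI summaries to all binary efficacy measures and makes no exception for the direction of the endpoint. Table JAIM.6.4 carries this into 13 rows. Among them are "Proportion of patients with worsening in each SLEDAI-2K individual organ system vs baseline" and "Proportion of patients with worsening in each BILAG individual organ system vs baseline". The first is a protocol secondary endpoint (Protocol Table JAIM.2); the BILAG individual organ analyses were added in SAP Version 3. Other rows state the same clinical idea in the favourable direction, for example "Proportion of patients with no new BILAG A and no more than 1 new BILAG B disease activity score" and the row for no worsening in the Physician's Global Assessment (PGA).

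Section 6.4.2.2 sets the NRI rule. It uses the composite strategy. Patients who permanently stop study treatment or take prohibited medication "are defined to have failed treatment for that particular visit interval", and operationally they "will be defined as non-responders for that visit interval and excluded from the subsequent visit intervals". Protocol Section 10.3.3.1 likewise says only that early discontinuers are nonresponders.

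Table JAIM.6.3 defines the observed variables. SLEDAI-2K organ improvement is met by patients "able to decrease SLEDAI-2K (from baseline) within each organ domain score, separately", and SLEDAI-2K organ worsening is worded as its mirror image. The missing-data column there gives item-level and domain-level rules, not NRI coding.

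**The concern.** In 11 of the 13 rows, non-responder and event absent are the same thing, so a programmer could write one shared rule: a non-responder has not met the row's condition. In the two worsening rows that rule would reverse its meaning. A patient who stops treatment or starts a prohibited drug would be reported as not worsened in every eligible organ, while failing the BILAG and PGA no-worsening rows. A patient eligible for both rows of one organ, say with arthritis present and myositis absent at baseline, would appear as neither improved nor worsened, that is, as stable. A patient with no postbaseline data would be reported as not worsened in the first interval.

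The triggering events are plausibly linked to worsening. Protocol Section 8.1.2 requires study treatment to stop before a non-permitted SLE agent is introduced, and it asks investigators to consider discontinuation when benefit is insufficient. The error would therefore make a protocol secondary endpoint look better than it is.

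**Working it through.** **Row count.** The rows with observed and NRI in Table JAIM.6.4 are: SRI-4; SRI-x (one row covering SRI-5 to SRI-8); SLEDAI-2K reduction of at least 4; SLEDAI-2K organ improvement; SLEDAI-2K organ worsening; no new BILAG A and at most one new B; BILAG organ improvement; BILAG organ worsening; PGA no worsening; BICLA; CLASI; LLDAS; EQ-5D-5L no problem. That makes 13, of which 2 count an unfavourable event.

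**Which coding the text supports.** Section 6.4.2.2 treats the intercurrent event as treatment failure. Counting the patient as not worsened gives a favourable result for a failed treatment, which contradicts that sentence. Counting the patient in the numerator agrees with it. The rival rule has to be inferred from the mirrored SLEDAI-2K wording in Table JAIM.6.3. Those cells define the observed variable and do not address imputation. The BILAG worsening entry is worded as an increment in grade and lacks the mirrored phrase.

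**Size of the coding choice.** For one organ and one visit interval, let d be the imputed share of analysed patients, w the worsening proportion in the others, and q the share of imputed patients who truly worsened in that organ. The documents give none of these, so all values are assumptions.

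- Event-absent coding: (1 − d)w
- Failure coding: (1 − d)w + d
- True organ worsening: (1 − d)w + dq
- Gap between codings: d
- Event-absent coding is too low by dq; failure coding is too high by d(1 − q)

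With w = 5% and q from 5% to 30%:

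| d | Event absent | Failure | True worsening |
|---|---|---|---|
| 2% | 4.9% | 6.9% | 5.0% to 5.5% |
| 10% | 4.5% | 14.5% | 5.0% to 7.5% |
| 20% | 4.0% | 24.0% | 5.0% to 10.0% |

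At d = 10%, event-absent coding is low by 0.10 × 0.05 = 0.5 points to 0.10 × 0.30 = 3.0 points. Failure coding is high by 0.10 × 0.95 = 9.5 points to 0.10 × 0.70 = 7.0 points. The two errors are equal when q = 50%; below that, failure coding lies further from organ worsening itself. The NRI version is therefore a composite of worsening or treatment failure, as the stated strategy intends. It is not an estimate of worsening alone.

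**Limit on d.** Under Section 6.4.2, imputation stays within a visit interval, and discontinued patients leave later intervals. At Week 156, the key time point, only events after Week 108 are imputed. Earlier discontinuations drop out of the denominator under either coding, so d is not the cumulative three-year dropout share.

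**The case for a change.** The best case for acting is that the silence is real and closing it is cheap. Two programmers following this SAP could report figures for the same patients that differ by d, and a reader could not tell which rule had been used. One sentence and two row labels would settle it, and the SAP's own estimand wording supplies the answer.

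Two parts of this stand. The SAP has no explicit mapping for these rows, and the NRI figures in them should be read as worsening or treatment failure, with one discontinuation counting in every organ for which the patient is eligible.

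The rest does not amount to a defect. The favourable coding needs an unwritten rule that conflicts with a written one. Spelling out failure coding would not make the rows a better measure of organ worsening: over the assumed range of q it moves them further from it. Whether to prefer the composite or the observed-case figure is a fair choice, and the SAP already produces both, with Section 6.4.2.1 stating that the observed-case summary is conditional on completing treatment to that visit. A rule that patients with a triggering event may never be counted as not worsened anywhere in the interval could also override on-treatment observations made earlier in it, because the footnote to Table JAIM.6.4 requires analysis at each visit. Further additions, such as a column of imputed counts or a carried-forward sensitivity analysis, would correct no wrong result.

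**Conclusion.** This is a missing detail that an analyst fills sensibly from Section 6.4.2.2: a patient who has failed treatment counts as a failure. The gap between the two possible codings is d, which is 2 to 20 points over the assumed range of 2% to 20%. The understatement of true worsening if the unsupported coding were used is smaller, 0.5 to 3.0 points at d = 10% and q of 5% to 30%. All these sizes rest on assumed values.

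The consequence is limited in any case. Section 6.1 rules out between-group inference unless otherwise stated, Section 6.11.2 says efficacy is not a primary outcome, and the observed-case figure accompanies the NRI figure in both rows. Programming specifications or a table footnote can record the coding; the SAP does not need to change for it.
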